11. ADMINISTRATIVE ASPECTS AND PUBLICATION

11.1 Handling and storage of data and documents

Patients will be included after verification of eligibility by the office of the department of hematology. A list of questions to be answered during the inclusion procedure is included in the registration check-list (see appendix D), including inclusion criteria and date of written informed consent. This check-list should be completed by the physician before the patient is included. Patients will be assigned for the purpose of the study and publication, a unique patient number (UPN).

Data will be recorded on Case Report Forms (CRF) and will be entered after validation into a computer system for subsequent tabulation and analyses. The data will be handled confidentially and, as far as possible, anonymously.

The investigator will retain the originals of the source documents generated for a minimum of ten years after the study is completed. After this all documents will be archived according to Good Clinical Practice (GCP) regulations. The results of the study will be published in recognized medical journals if applicable. If so, the patient identity will not be revealed.

11.2 Annual progress report

The principal investigator will submit a summary of the progress of the trial to the CCMO once a year. Information will be provided on the date of inclusion of the first subject, numbers of subjects included and numbers of subjects that have completed the trial, serious adverse events/serious adverse reactions, other problems, and amendments.

11.3 End of study report

The investigator will notify the CCMO of the end of the study within a period of 8 weeks. The end of the study is defined as the last patients' last control visit. This will be 6 months after the infusion of CMV pp65-specific T cells of patient number 15 or at time of subsequent DLI of patient number 15.

In case the study is ended prematurely, the investigator will notify the CCMO including the reason for the premature termination.

Within one year after the end of the study, the investigator will submit a final study report with the results of the study, including any publications/abstracts of the study, to the CCMO.

11.4 Public disclosure and publication policy

A writing committee will be responsible for the publication of the results of this study.

APPENDIX A

WHO performance score

- 0 Normal activity
- 1 Symptoms, but nearly ambulatory
- 2 Some bed time, but to be in bed less than 50% of normal daytime
- 3 Needs to be in bed more than 50% of normal daytime
- 4 Unable to get out of bed

APPENDIX B

Common toxicity Criteria

The grading of toxicity and adverse events will be done using the NCI Common Terminology Criteria for adverse events, CTC version 4.0, published May 28, 2009. A complete document (78 pages) may be downloaded from the following site:

http://evs.nci.nih.gov/ftp1/CTCAE/CTCAE_4.03_2010-06-14_QuickReference_8.5x11.pdf

APPENDIX C

Grading of GvHD

Acute GvHD

Staging of acute GvHD

	Skin	Liver	Gastrointestinal
0	No rash	Bilirubin < 2 mg / dl (< 34 umol/L)	Diarrhea < 500 ml/day
1	Maculopapular rash on < 25% of body surface	Bilirubin 2-3 mg/dl (34-50 umol/L)	Diarrhea 500-1000 ml/day
2	Maculopapular rash on 25-50% of body surface	Bilirubin 3-6 mg/dl (51-102 umol/L)	Diarrhea 1000-1500 ml/day
3	Generalized erythroderma	Bilirubin 6-15 mg/dl (103-225 umol/L)	Diarrhea > 1500 ml/day
4	Generalized erythro- derma with formation of bullae and desquamation	Bilirubin > 15 mg/dl (> 225 umol/L)	Severe abdominal pain with or without ileus

Grading of acute GvHD

Overall grade	Stage		
	Skin	Liver	Gut
I (mild)	1 or 2	0	0
II (moderate)	1-3	1	1
III (severe)	2 or 3	2 or 3	2 or 3
IV (life-threatening)	2-4	2-4	2-4

Chronic GvHD

Limited Localized skin involvement and/or liver function abnormalities

Extensive Generalized skin involvement or localized skin involvement and/or liver function abnormalities + other organ involvements

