7.3 Evaluation criteria

7.3.1 Safety evaluation after treatment

General non GvHD toxicity will be scored according to the NCI Common Terminology Criteria for Adverse Events (CTCAE) Version 4.0 (see appendix B) In case of grade 3 or 4 toxicity after infusion of CMV pp65-specific T cells, further administrations of CMV pp65-specific T cells will be cancelled in that patient.

Acute GvHD will be graded using the criteria outlined in appendix C. In case of grade 3 or 4 acute overall GvHD after infusion of CMV pp65-specific T cells, further administrations of CMV pp65-specific T cells will be cancelled in that patient.

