7.5 Premature termination of the study

In case of increase of >1 point of overall grade acute GvHD in 2 out of the first 3 patients, or 3 out of the first 6 patients, or 4 out of the first 10 patients, the study will be closed temporarily for inclusions and the outcomes in all patients will be discussed in order to decide whether potential beneficial effects of the treatment could overcome non-beneficial effects of GvHD.

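### Appendix C prints the limit between liver GvHD stages 3 and 4 as 15 mg/dl and as 225 umol/L, which are not the same bilirubin; the unit used could change the overall grade in a narrow range

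*Protocol*

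**What the plan says.** Section 7.3.1 makes Appendix C the grading instrument: "Acute GvHD will be graded using the criteria outlined in appendix C". The liver column of its staging table gives bilirubin limits in mg/dl, with umol/L in brackets:

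- Stage 0: "Bilirubin < 2 mg / dl (< 34 umol/L")
- Stage 1: "Bilirubin 2-3 mg/dl (34-50 umol/L")
- Stage 2: "Bilirubin 3-6 mg/dl (51-102 umol/L")
- Stage 3: "Bilirubin 6-15 mg/dl (103-225 umol/L")
- Stage 4: "Bilirubin > 15 mg/dl (> 225 umol/L")

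A second table in Appendix C turns organ stages into an overall grade. For skin, liver and gut, the grade III row reads "2 or 3 2 or 3 2 or 3". The grade IV row admits stages 2 to 4 in each organ.

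The overall grade is used in four places:

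- Section 5.4 bars infusion at grade III or above.
- Section 7.3.1 cancels a patient's further infusions at grade 3 or 4.
- Section 9.4 tabulates grade III or more.
- Section 7.5 pauses inclusion on an "increase of >1 point of overall grade acute GvHD in 2 out of the first 3 patients", or in 3 of the first 6, or 4 of the first 10.

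**The concern.** When a table gives one limit in two units, both figures should mark the same point. Here the limit between liver stages 3 and 4 does not. Two assessors who both follow Appendix C could stage the same bilirubin differently, depending on the unit in the laboratory report. The protocol does not say which unit governs.

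This matters because acute GvHD is part of the first listed endpoint (section 7.1) and is the potential risk named in section 10.3. Its overall grade also drives the study-level pause in section 7.5. That rule counts rises of more than one grade, so a shift between grades III and IV can decide whether a patient counts.

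**Working it through.** **Inputs.** All come from the liver column of Appendix C. No outside conversion factor is needed.

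**Step 1: the factor behind each printed limit (umol/L divided by mg/dl).**

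| Limit (mg/dl) | Printed umol/L | Factor |
|---|---|---|
| 2 | 34 | 34/2 = 17.0 |
| 3 (end of stage 1) | 50 | 50/3 = 16.67 |
| 3 (start of stage 2) | 51 | 51/3 = 17.0 |
| 6 (end of stage 2) | 102 | 102/6 = 17.0 |
| 6 (start of stage 3) | 103 | 103/6 = 17.17 |
| 15 (end of stage 3, start of stage 4) | 225 | 225/15 = 15.0 |

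The 50 and 103 are the whole numbers next to 51 and 102, so these limits all agree with a factor of 17 to within 1 umol/L.

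**Step 2: can 225 be reproduced from the table's own factor?** No.

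- At 17.0: 15 × 17 = 255 umol/L.
- At the lowest factor in the other rows, 16.67: 15 × 16.67 = 250 umol/L.
- At the highest, 17.17: 15 × 17.17 = 257.5 umol/L.

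The gap at factor 17 is 255 − 225 = 30 umol/L, or 30/255 = 12%. Rounding does not explain it.

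**Step 3: the printed 225 umol/L in mg/dl.** 225/17 = 13.2 mg/dl (13.1 to 13.5 over the factors 17.17 to 16.67).

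**Step 4: the range in conflict.** Above 225 and up to about 255 umol/L (about 13.2 to 15 mg/dl), the umol/L limit gives stage 4 and the mg/dl limit gives stage 3. Example: 240 umol/L is 240/17 = 14.1 mg/dl.

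**Step 5: from stage to overall grade.** Liver stage 4 appears only in the grade IV row. Liver stage 3 appears in both the grade III and the grade IV row. The unit could therefore move a patient between III and IV, but need not.

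**Step 6: from grade to the pause rule.** This takes the grade at infusion as the baseline, which section 7.5 does not spell out.

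| Grade at infusion | Rise to III | Rise to IV | Does III versus IV alter the count? |
|---|---|---|---|
| 0 | +3, counts | +4, counts | No |
| I | +2, counts | +3, counts | No |
| II | +1, does not count | +2, counts | Yes |
| III or IV | not infused (section 5.4) | not infused | Does not arise |

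**Step 7: the other uses of the grade.** Sections 5.4, 7.3.1 and 9.4 all treat III and IV alike, so the unit makes no difference there.

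**The case against.** The arithmetic is hard to dispute. The figure 225 stands in two separate cells, so a misread character in the PDF is an unlikely explanation. The case on the other side is about consequence, and most of it stands.

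- **Stage 3 is not tied to grade III.** The grade III row lies wholly inside the grade IV row, and the table does not say whether a row needs all three organs or any one. A patient with stage 4 skin or gut is grade IV whichever unit is used. This overlap is a separate ambiguity that correcting the bilirubin figure would not remove.
- **A reader might infer that the reported split between grades III and IV depends on the unit.** The protocol plans no such split. Section 9.4 tabulates grade III or more as one category.
- **A reader might infer that the pause-rule count does change for patients infused at grade II.** It only could. Such a patient must also have bilirubin in the narrow range, must not be grade IV on other grounds, must be among the first 10, and must be the deciding case at a look. The consequence is then a temporary closure with discussion of outcomes, and section 9.5 already plans interim analyses after 3, 6 and 10 patients.
- **A reader might infer that patients will be staged in conflicting units.** The documents do not show this. Infusion takes place at one centre (section 5.2), and the laboratory's reporting unit is not given. If one unit is used throughout, patients are staged consistently with one another. The limit applied still differs according to which unit that is.

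None of this removes the contradiction. The table states two different limits as one, and the protocol gives no means of choosing between them.

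**Conclusion.** The point holds, at low severity. Appendix C gives two limits between liver stages 3 and 4 that differ by about 30 umol/L (25 to 32.5 over the factors implied by its other rows). A bilirubin above 225 and up to about 255 umol/L gets a different liver stage in each unit, and the overall grade could follow.

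Of the rules that use the grade, only the pause count in section 7.5 could be affected, and only for a patient infused at grade II who is not grade IV on other grounds. The sample size, the response endpoint, the planned toxicity tabulation and the individual-patient rules are untouched.

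The verdict rests on the table's own conversion factor and on reading the rise in section 7.5 from the grade at infusion. The documents do not give the share of patients in the range; it is probably small. They also do not show which of the two printed figures was intended, and this review takes no view on which limit is clinically right.

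**What to change.** Reconcile the two units in both the stage 3 and the stage 4 liver cells of Appendix C, and state which unit governs staging. A straight conversion of the printed 15 mg/dl at the table's own factor gives 255 umol/L. If 225 umol/L was the intended limit, the mg/dl figure is the one that must change. The sponsor should confirm which it is. If any patient has already been graded with a bilirubin in the range, recheck the liver stage, the overall grade and the pause-rule count.

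The cost is two table cells and one sentence. No new data, visits or procedures are needed.

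### Appendix C does not separate overall acute GvHD grades III and IV, does not say how the organ columns combine, and gives two different bilirubin limits between liver stages 3 and 4

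*Protocol*

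**What the plan says.** Appendix C stages skin, liver and gut from 0 to 4 and then maps the three stages to an overall grade. With columns in the order skin, liver, gut, the two upper rows are "III (severe) 2 or 3 2 or 3 2 or 3" and "IV (life-threatening) 2-4 2-4 2-4". No further column, footnote or tie-break separates them, and nothing says how the three columns combine.

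The liver limits are given in two units: "Bilirubin < 2 mg / dl (< 34 umol/L" for stage 0, "Bilirubin 2-3 mg/dl (34-50 umol/L" for stage 1, "Bilirubin 3-6 mg/dl (51-102 umol/L" for stage 2, "Bilirubin 6-15 mg/dl (103-225 umol/L" for stage 3 and "Bilirubin > 15 mg/dl (> 225 umol/L" for stage 4.

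Four rules use the overall grade:
- Section 5.4: grade III or higher is a contraindication to infusion.
- Section 7.3.1: grade 3 or 4 after infusion cancels further infusions in that patient.
- Section 9.4: the main toxicity tabulation counts grade III or more.
- Section 7.5 and the Summary: the study pauses temporarily at set counts. The rule begins "In case of increase of >1 point of overall grade acute GvHD in 2 out of the first 3 patients" and continues with 3 of the first 6 and 4 of the first 10.

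**The concern.** A grading table has to give each patient one grade. If two rows overlap completely, or the columns can be combined in two ways, two assessors can grade the same findings differently and both be following the protocol.

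Acute GvHD is the one potential risk named in section 10.3 and the only trigger of the pause rule. The trial is open-label with a single treatment, and the principal investigator performs the interim analyses (section 9.5). With thresholds of 2 of 3, 3 of 6 and 4 of 10, one reclassified patient can decide whether the study pauses. These decisions are taken during the trial, so a later analysis plan cannot repair the table.

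**Working it through.** **Inputs.** The stage ranges and bilirubin limits are from Appendix C; the rules are from sections 5.4, 7.3.1, 7.5 and 9.4.

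**1. Bilirubin.** Factor = umol/L divided by mg/dl.

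| mg/dl | umol/L in the table | factor | mg/dl × 17 |
|---|---|---|---|
| 2 | 34 | 17.0 | 34 |
| 3 | 51 (stage 1 ends at 50) | 17.0 | 51 |
| 6 | 102 (stage 3 starts at 103) | 17.0 | 102 |
| 15 | 225 | 15.0 | 255 |

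The first three limits reproduce at 17; the fourth does not. At the table's own factor, 15 mg/dl is 255 umol/L, and 225 umol/L is 225/17 = 13.2 mg/dl. An assumed factor of 17.1 gives 256.5 and also 13.2. A value of 226 to 255 umol/L is thus stage 4 by the umol/L limit and stage 3 by the mg/dl limit.

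**2. Overlap of grades III and IV.** Three organs with five stages each give 5³ = 125 patterns, 124 of them non-zero. Two readings are possible.

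*'And'* (all three organs within the row's range):
- Grade I: 2 × 1 × 1 = 2 patterns.
- Grade II: 3 × 1 × 1 = 3 patterns.
- Grade III: 2³ = 8 patterns.
- Grade IV: 3³ = 27 patterns, including all 8 of grade III, so 27 − 8 = 19 are grade IV only.

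*'Or'* (at least one involved organ within the row's range):
- Grade III: 125 − 3³ = 98 patterns, since 3 stages per organ (0, 1, 4) miss the row.
- Grade IV: 125 − 2³ = 117 patterns, since 2 stages per organ (0, 1) miss the row. All 98 of grade III are included.

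No pattern is grade III only under either reading.

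**3. Missing and/or rule.**

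| | 'and' | 'or' |
|---|---|---|
| Grade III or more, of 124 | 27 | 117 |
| No grade, of 124 | 124 − (2 + 3 + 27) = 92 | 0 |

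The 27 lie within the 117, so 117 − 27 = 90 patterns cross the grade III line depending on the reading. Isolated gut stage 3 has no grade under 'and' and meets both III and IV under 'or'. Isolated skin stage 2 is exactly the grade I row under 'and', but meets all four rows under 'or'.

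**4. Which rules each defect reaches.** The contraindication, the cancellation rule and the toxicity table all pool III and IV, so the overlap in step 2 cannot change them. In the pause rule, taking the grade before infusion as the baseline:

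| Grade before infusion | Rise to III | Rise to IV |
|---|---|---|
| 0 | 3 points, counts | 4 points, counts |
| I | 2 points, counts | 3 points, counts |
| II | 1 point, does not count | 2 points, counts |

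A patient at III or above may not be infused. The overlap therefore matters only from grade II. The bilirubin window moves the liver only between stages 3 and 4. Neither reading lets that move a patient across the grade III line, so it bears on the III/IV boundary alone. The missing and/or rule does cross that line and reaches all four rules.

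**The case against.** The strongest reply is that the practical effect is small. Three of the four rules pool grades III and IV, and the pause rule is a temporary closure with discussion of all outcomes, not an automatic stop. A sensible assessor could also read the rows in order: grade III unless some organ is at stage 4. Under 'and', 2 + 3 + 19 = 24 of the 32 gradable patterns already have exactly one grade.

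Much of this stands. A reader might infer that the III/IV overlap and the bilirubin mismatch disturb the contraindication, the cancellation rule and the toxicity table. They do not, because of the pooling. The row-order reading would resolve the overlap, but it is not stated. The opposite convention, taking the highest row met, leaves grade III empty. Neither convention supplies the and/or rule, and the pooling does not protect against that gap.

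A reader might also infer that gut stages in absolute ml/day under-stage small children, since eligibility starts at age 0. The documents do not support this. Nothing in them contradicts absolute volumes, they contain no paediatric standard to compare with, and a different staging would be a clinical criterion outside this review.

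A fault in reading the PDF is unlikely to explain the findings. The value 225 appears in both the stage 3 and stage 4 rows, and the nested ranges repeat across all three organ columns.

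**Conclusion.** The table is wrong as written and should be fixed. There are three defects with different reach:

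- **Grades III and IV overlap completely** (8 of 8 patterns under 'and', 98 of 98 under 'or'). The effect is confined to the pause rule for a patient at grade II before infusion.
- **No and/or rule is stated** (27 against 117 of 124 patterns at grade III or more; 92 without a grade under 'and'). This reaches the contraindication, the cancellation rule, the toxicity table and the pause rule, and is the most consequential of the three.
- **The 15 mg/dl limit is paired with 225 umol/L**, where the table's own factor gives 255. The window is 226 to 255 umol/L and bears only on the III/IV boundary.

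The counts are of possible stage patterns, not of expected patients; the protocol gives no frequencies by pattern. The pause-rule result assumes that the rise is measured from the grade before infusion. The arithmetic shows that the two bilirubin units disagree, but not which of them was intended.

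**What to change.** In Appendix C:
1. Reconcile the overall-grade rows so that each combination of skin, liver and gut stages maps to exactly one grade.
2. State how the organ columns combine.
3. Reconcile the two bilirubin units at the stage 3/4 boundary, in both rows where 225 appears, and name the unit that governs.

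The sponsor decides which clinical limits apply; the request is only that the table agree with itself. A simple check is to list all 125 patterns and confirm one grade for each non-zero pattern. If patients have already been graded, the recorded organ stages and bilirubin values should be regraded under the reconciled table.

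The cost is one appendix page. No additional data need be collected, and the sample size does not change.

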APPENDIX D

Standard indications for alloSCT including:

In adults:

Acute lymphoblastic leukemia/lymphoma
Acute myeloid leukemia
Chronic lymphocytic leukemia
Chronic myelogenous leukemia
Hodgkin lymphoma
Non Hodgkin lymphoma
Myelodysplastic syndromes
Myeloproliferative neoplasms
Plasma cell myeloma
Severe aplastic anemia
Sicklecell disease
Thalassemia

In children:

Acute lymphoblastic leukemia/lymphoma
Acute myeloid leukemia
Chediak-Higashi syndrome
Chronic myelogenous leukemia
Congenital immunodeficiencies
Diamond-blackfan anemia
Fanconi anemia
Griscelli-Siccardi syndrome
Hemophagocytic lymphohistiocytosis
Juvenile myelomonocytic leukemia
Myelodysplastic syndromes
Non Hodgkin lymphoma
Paroxysmal nocturnal hemoglobinuria
Resistent Langerhans histiocytosis
Severe aplastic anemia
Thalassemia
